10.1. Software for Data Capture

Data will be entered into a data capture system provided by TraCS Clinical Research Data Management Service (REDCap). REDCap is a 21 CFR Part 11-compliant data capture system provided by the NC TraCS Institute at UNC. The data system includes password protection and internal quality checks, such as automatic range checks, to identify data that appear inconsistent, incomplete, or inaccurate.

10.2. Responsibilities for Data Capture and Database Management

Data collection is the responsibility of the clinical trial staff at the site under the supervision of the site investigators (principal investigator and co-investigator). The investigator is responsible for ensuring the accuracy, completeness, legibility, and timeliness of the data reported.

Hardcopies of the study visit worksheets will be provided for use as source document worksheets for recording data for each participant enrolled in the study. Data recorded in the electronic case report form (eCRF) derived from source documents should be consistent with the data recorded on the source documents.

Clinical data (including adverse events (AEs), concomitant medications, and expected adverse reactions data) will be entered into REDCap. The data system includes password protection and internal quality checks, such as automatic range checks, to identify data that appear inconsistent, incomplete, or inaccurate. Clinical data will be entered directly from the source documents. Trained research personnel (including the co-investigator) will have complete access to the REDCap system, while the principal investigator will have read-only ability.

10.3. Study Records Retention

According to the University of North Carolina at Chapel Hill's Archives and Record Management Services schedule for General Records Retention and Disposition Schedule 6.10, records will be kept for 5 years after the completion of the study or grant end date, whichever is later.

11. Collection and Management of Tissue Specimens

Not applicable.

12. Safety Monitoring and Management

12.1. Risk / Benefit Assessment

Potential Risks:

Risk of Confidentiality Breach: To avoid the uncommon event breaches in confidentiality, study documents that contain personal information, including the informed consent document, will be kept in locked filing cabinets in locked rooms. The document that links study ID numbers to personal identifying information will be a password-protected spreadsheet. All data is stored in locked cabinets inside locked offices; electronic data will be stored only on password-protected computers, and data encryption methods will be used during communication between investigators. Interviews will be conducted over the HIPAA approved Zoom account. Only study personnel will have access to the data. All study staff participate in annual human participant training that includes education about responsibilities to minimize risk of confidentiality breach.

Risk of Embarrassment: Self-report assessments contain questions regarding sensitive personal information. This uncommon risk is necessary in order to assess for relevant preexisting disorders. Participants will be assured upon intake that only study personnel will see any clinical ratings and that self-identifying information will not be collected alongside HIPAA protected information.

Risk of Injury and Discomfort:

The side effects of tACS are mild and transient; in fact, low intensity transcranial current stimulation, such as tACS, has been used for several years without any report of serious side effects. Furthermore, this stimulation mode has nothing to do with electroconvulsive therapy that applies many orders of magnitude higher stimulation current. Rather, transcranial current stimulation is so weak that it does not cause super-threshold activation of neurons. TACS does have some mild side effects, such as transient tingling, burning, pulsing sensation, or itching under the electrode sites (common). In a previous tACS trial we conducted, participants from all three groups of stimulation (two stimulation conditions, one was an active placebo group) reported either absent or mild side effects, and there was no difference between the groups with the exception of “flickering lights” (or phosphene, $p = 0.014$). To monitor these mild side effects, we will be administering a stimulation questionnaire after each stimulation session to determine whether these effects were experienced and at what intensity. Research personnel is present during the full experiment. There have also been infrequent reports of reduced ability to focus, change in cognition, altered mood, headaches, and sleepiness. There is no evidence available that indicates that these potential side-effects are associated with stimulation versus study participation in general. In our previous depression work, we found no signal that supports an association between any of these side-effects and the administration of tACS. Both the application of the tACS and the EEG electrodes can cause mild inconvenience such as mild headaches from the pressure of applying the electrodes.

The motor thresholding procedure that uses TMS has been used without reports of any serious side-effects. Some subjects report muscle twitching during stimulation and sometimes a headache (common, <50% incidence), but these possible effects are transient and do not persist after we stop stimulation. The transcranial stimulator used in this study was cleared by UNC Hospital Medical Engineering, the in-house engineering team of UNC hospitals that test the safety of medical devices. This TMS device has been cleared by the FDA for some indications, such as Major Depressive Disorder in patients, but it has not been evaluated by the FDA for this study. To mitigate

uncomfortable side effects, during the study, we will ask about participants' comfort, and their participation will immediately be stopped if they are experiencing discomfort. In theory, there is a possibility that application of magnetic fields could induce a seizure. However, this has never been reported as occurring in general. In the broader field of TMS research, including riskier procedures than just motor thresholding, estimates of all seizure incidence is <0.02%, but due to its implausibility and theoretical nature, experts estimate that the likelihood of seizure during motor thresholding is much lower than this number. In the unlikely event of this occurring, trained medical professionals, including an expert in epilepsy and emergency seizure response, are on-site to respond. Furthermore, in order to mitigate this risk, we use multiple strategies. First, we screen participants based from participating in the study that present with any traits that may lower their seizure threshold or pose increased risk of seizure. These contraindications are well documented within the field and updated guidelines are released approximately every 10 years with the latest recommendation released in 2020 (Rossi et al. 2020). Contraindications screening is conducted during phone screening prior to the TMS session. Second, we have chosen our stimulation parameters to be within recommended safety guidelines. Third, we document regular trainings for personnel performing the motor thresholding procedure that matches standards recommended by expert consensus (Rossi et al. 2020, Fried et al. 2021). Fourth, we employ a comprehensive monitoring and adverse event assessment in each participant.

Rossi S, Simone Rossi, Simone Rossi, Antal A, Bestmann S, Bikson M, Brewer CC, Brockmöller J, Carpenter LL, Cincotta M, et al. Safety and recommendations for TMS use in healthy subjects and patient populations, with updates on training, ethical and regulatory issues: Expert Guidelines. *Clinical Neurophysiology*. 2020;132(1):269–306. doi:10.1016/j.clinph.2020.10.003

Potential Benefits:

This study has not been designed to benefit the individual participants. However, the results from this study might be used to develop future interventions using non-invasive brain stimulation.

12.2. Assessment of Safety

If the participant indicates a non-zero answer to the question about suicide on the PHQ-9, a psychiatrist or clinical psychologist will be consulted with regards to next steps.

12.3. Unanticipated Problems, Adverse Events, Serious Adverse Events

Unanticipated Problems:

The Office for Human Research Protections (OHRP) considers unanticipated problems involving risks to participants or others to include, in general, any incident, experience, or outcome that meets all of the following criteria:

- Unexpected in terms of nature, severity, or frequency given (a) the research procedures that are described in the protocol-related documents, such as the Institutional Review Board (IRB)-approved research protocol and informed consent document; and (b) the characteristics of the participant population being studied;

- Related or possibly related to participation in the research (“possibly related” means there is a reasonable possibility that the incident, experience, or outcome may have been caused by the procedures involved in the research); and
- Suggests that the research places participants or others at a greater risk of harm (including physical, psychological, economic, or social harm) than was previously known or recognized.

Adverse Event (AE) Definitions:

Adverse event means any untoward medical occurrence associated with the use of an intervention in humans, whether considered intervention-related (21 CFR 312.32 (a)).

Serious Adverse Events (SAE) Definition: <insert text>

An adverse event (AE) or suspected adverse reaction is considered "serious" if, in the view of the investigator, it results in any of the following outcomes: death, a life-threatening adverse event, inpatient hospitalization or prolongation of existing hospitalization, a persistent or significant incapacity or substantial disruption of the ability to conduct normal life functions, or a congenital anomaly/birth defect. Important medical events that may not result in death, be life-threatening, or require hospitalization may be considered serious when, based upon appropriate medical judgment, they may jeopardize the participant and may require medical or surgical intervention to prevent one of the outcomes listed in this definition. Examples of such medical events include allergic bronchospasm requiring intensive treatment in an emergency room or at home, blood dyscrasias or convulsions that do not result in inpatient hospitalization, or the development of drug dependency or drug abuse.

Grading the Severity of Adverse Events and Events of ‘Special Interest’:

All adverse events (AEs) will be assessed by the principal investigator and/or co-investigator(s) using the following guidelines:

- **Mild** – Events require minimal or no treatment and do not interfere with the participant’s daily activities.
- **Moderate** – Events result in a low level of inconvenience or concern with the therapeutic measures. Moderate events may cause some interference with functioning.
- **Severe** – Events interrupt a participant’s usual daily activity and may require systemic drug therapy or other treatment. Severe events are usually potentially life-threatening or incapacitating. Of note, the term “severe” does not necessarily equate to “serious”.

Relatedness Definition:

All adverse events (AEs) must have their relationship to study intervention assessed by the principal investigator and co-investigator(s) who examines and evaluates the participant based on temporal relationship and their clinical judgment. The degree of certainty about causality will be graded using the categories below. In a clinical trial, the study product must always be suspect.

- **Definitely Related** – There is clear evidence to suggest a causal relationship, and other possible contributing factors can be ruled out. The clinical event, including an abnormal laboratory test result, occurs in a plausible time relationship to study intervention administration and cannot be explained by concurrent disease or other drugs or chemicals. The response to withdrawal of the study intervention (dechallenge) should be clinically plausible. The event must be pharmacologically or phenomenologically definitive, with use of a satisfactory rechallenge procedure if necessary.
- **Probably Related** – There is evidence to suggest a causal relationship, and the influence of other factors is unlikely. The clinical event, including an abnormal laboratory test result, occurs within a reasonable time after administration of the study intervention, is unlikely to be attributed to concurrent disease or other

drugs or chemicals, and follows a clinically reasonable response on withdrawal (dechallenge). Rechallenge information is not required to fulfill this definition.

- **Potentially Related** – There is some evidence to suggest a causal relationship (e.g., the event occurred within a reasonable time after administration of the trial medication). However, other factors may have contributed to the event (e.g., the participant's clinical condition, other concomitant events). Although an AE may rate only as "possibly related" soon after discovery, it can be flagged as requiring more information and later be upgraded to "probably related" or "definitely related", as appropriate.
- **Unlikely to be related** – A clinical event, including an abnormal laboratory test result, whose temporal relationship to study intervention administration makes a causal relationship improbable (e.g., the event did not occur within a reasonable time after administration of the study intervention) and in which other drugs or chemicals or underlying disease provides plausible explanations (e.g., the participant's clinical condition, other concomitant treatments).

Not Related – The AE is completely independent of study intervention administration, and/or evidence exists that the event is definitely related to another etiology. There must be an alternative, definitive etiology documented by the clinician.

Expectedness Definition:

The principal investigator, with input from the co-investigator when necessary, will determine whether an adverse event (AE) is expected or unexpected in this population. The principal investigator is an expert in non-invasive brain stimulation and will provide his expert opinion regarding this as well. An AE will be considered unexpected if the nature, severity, or frequency of the event is not consistent with the risk information previously described for the study intervention.

AE and SAE Assessment, Follow-up Procedures:

The occurrence of an adverse event (AE) or serious adverse event (SAE) may come to the attention of study personnel during study visits, or the study participant may report AE or SAEs outside of a scheduled study visit. All AEs including local and systemic reactions not meeting the criteria for SAEs will be captured on the appropriate case report form (CRF). Information to be collected includes event description, time of onset, clinician's assessment of severity, relationship to study product (assessed only by those with the training and authority to make a diagnosis), and time of resolution/stabilization of the event. All AEs occurring while on study must be documented appropriately regardless of relationship. All AEs will be followed to adequate resolution. Any medical condition that is present at the time that the participant is screened will be considered as baseline and not reported as an AE. However, if the study participant's condition deteriorates at any time during the study, it will be recorded as an AE. Changes in the severity of an AE will be documented to allow an assessment of the duration of the event at each level of severity to be performed. AEs characterized as intermittent require documentation of onset and duration of each episode.

Reporting and Documentation Procedures:

| What event is reported | When is event reported | By whom is event reported | To whom is event reported |
|---|---|---------------------------|---------------------------|
| Fatal or life-threatening unexpected, suspected serious adverse reactions | Within 24 hours of initial receipt of information | Investigator | Local/internal IRB |
| Non-fatal, non-life-threatening unexpected, suspected serious adverse reactions | Within 48 hours of initial receipt of information | Research Personnel | Local/internal IRB |

| | | | |
|--|---|--------------|--------------------|
| Unanticipated adverse device effects | Within 10 working days of investigator first learning of effect | Investigator | Local/internal IRB |
| Unanticipated Problem that is not an SAE | Within 7 days of the investigator becoming aware of the problem | Investigator | Local/internal IRB |

Participant Notification of New Information:

Any new information gained during the study that may affect a participant's willingness to continue in the study will be reported to all currently enrolled participant.

12.4. Safety Monitoring

Research personnel will record all reportable events with start dates occurring any time after informed consent is obtained until the last day of study participation. At each study visit, research personnel will inquire about the occurrence of AE/SAEs since the last visit. All AEs including local and systemic reactions not meeting the criteria for SAEs will be captured on the appropriate case report form (CRF). Information to be collected includes event description, time of onset, clinician's assessment of severity, relationship to study product (assessed only by those with the training and authority to make a diagnosis), and time of resolution/stabilization of the event. All AEs will be followed to adequate resolution.

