5.1. Numbers of Participants

5.1.1. Number to be screened: $N \leq 100$

5.1.2. Number to be enrolled: $N \leq 50$

The sample size is 28 participants in the final dataset, i.e. the participants who completed all the visits for the primary outcomes, i.e. Visits 1, 2, 3, 4, 5, 6, 7 (including the three nights with EEG). However, to ensure that 28 participants complete the experiment, we conservatively estimate to screen 100 participants and to enroll 50 participants as a ceiling for the sake of IRB approval. The motivation for the sample size of 28 participants is the following power analysis: power analysis: $dz = 0.5$, $1-\beta = 0.80$, $\alpha = 0.05$. Participants who drop-out or have missing data will be replaced.

Recruitment takes place in the general population.

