7.4. Study Visits

Visit 2 (day after Visit 1; afternoon/early evening, i.e. start between 12pm and 6pm)

1. Questioning whether there has been any use of alcohol, psychotropic substances or illicit drugs during the past 24 hours. If yes, study participation is terminated.
2. Questions to assess current sleepiness and mood, as this may affect the results of further testing:
 - 2.1 Questions for sleep quality the night before
 - 2.2 Karolinska Sleepiness Scale (24)
 - 2.3 Positive And Negative Affect Schedule (PANAS) (25)
3. Motor thresholding by TMS.
4. Thresholding individual tACS amplitude.
5. Gamma-tACS or control stimulation (according to randomization) during the following cognitive tests, presented on a computer screen (2 minutes of resting EEG without stimulation after each test; total duration approximately 40 minutes):
 - 5.1 Rey Auditory Verbal Learning Test (RAVLT, version 1) (26)
 - 5.2 Letter Fluency; letters F, A, S (28)
 - 5.3 Stroop Color and Word Test (29)
 - 5.4 Trail Making Test A and B (30)

- 5.5 Word association test; version 1
- 5.6 Four subtests of the Test of Attentional Performance (TAP) (31): Alertness, Go/Nogo, Divided Attention, Visual Scanning
- 5.7 RAVLT delayed recall
6. Evaluation of side effects with open question (“Did you feel anything particular or note anything special during this session?”)
7. The participant will be given the sleep diary for the second night with the EEG headband.

Visit 3 (day after Visit 2; morning, i.e. start between 8am and 12pm)

1. Questioning whether there has been any use of alcohol, psychotropic substances or illicit drugs during the past 24 hours. If yes, the participant is excluded.
2. Questions to assess current sleepiness and mood, as this may affect the results of further testing:
 - 3.1 Questions for sleep quality the night before
 - 3.2 Karolinska Sleepiness Scale
 - 3.3 Positive And Negative Affect Schedule (PANAS)
3. Cognitive follow-up testing
 - 4.1 RAVLT “ultra-delayed” recall; version 1
 - 4.2 Letter fluency; letters B, H, R
 - 4.3 Stroop Color and Word Test (SCWT)
 - 4.4 Trail Making Test Part A and B
 - 4.5 Word association recall; version 1
 - 4.6 Four subtests of the Test of Attentional Performance (TAP): Alertness, Go/NoGo, Divided Attention, Visual Scanning

Visit 4 (telephone; 5 days after Visit 2)

Performed by telephone.

1. Assessment of adverse events.
2. RAVLT “ultra-delayed” recall; version 1.
3. Word association recall; version 1.

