 - 4.6 Four subtests of the Test of Attentional Performance (TAP): Alertness, Go/NoGo, Divided Attention, Visual Scanning

Visit 7 (telephone; 5 days after Visit 5)

Performed by telephone.

1. Assessment of adverse events.
2. RAVLT “ultra-delayed” recall.
3. Word association recall; version 2.

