7.5. Early Discontinuations

Data to be Collected

If the study participation has to be terminated early by the investigators (due to safety concerns), or if a participant chooses to withdraw from the study, including the case of not showing up for scheduled visits on site (Visits 1, 2, 3, 5, 6), the data collected to date will not be included for the cognitive and sleep-EEG outcomes and the participant will be replaced. However, early discontinuation will be included in the data set for the feasibility outcomes as appropriate. Visits 4 and 7 are not mandatory for study completion.

Criteria for Intervention Discontinuation

An investigator may discontinue or withdraw a participant from the study for the following reasons:

- Any clinical adverse event (AE), intercurrent illness or other medical condition, or situation occurs such that continued participation in the study would not be in the best interest of the participant.

- The participant meets any exclusion criteria (either newly developed or not previously recognized) or a reason for immediate early termination of participation.

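### Adverse-event recording stops when participation ends, so people who leave just after a stimulation or miss Visit 7 have 0 to 1 day of scheduled safety coverage instead of 5

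*Combined protocol and SAP*

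**What the plan says.** **Recording window.** Section 12.4 collects events with "start dates occurring any time after informed consent is obtained until the last day of study participation". The last day of participation is not defined, and no number of days after TMS or tACS is given. Section 12.4 adds: "At each study visit, research personnel will inquire about the occurrence of AE/SAEs since the last visit".

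**Schedule.** The Table of Events (7.1) marks adverse-event assessment at Visits 2 to 7. Visits 4 and 7 are telephone calls 5 days after the first and second stimulation, and in 7.4 each opens with "Assessment of adverse events" before the recall tests.

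**Status of the calls.** Section 7.5 states: "Visits 4 and 7 are not mandatory for study completion". Section 5.1.2 defines the 28 participants in the final dataset as those who "completed all the visits for the primary outcomes, i.e. Visits 1, 2, 3, 4, 5, 6, 7".

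**Early exit.** Section 7.5 lists a clinical adverse event among the reasons for discontinuing a participant. The TMS text in 12.1 says participation is stopped at once if there is discomfort. For those who leave, 7.5 covers which data are used and that the participant is replaced; it describes no safety contact. Section 7.6 provides an attempt at contact after a no-show.

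**The concern.** The window is tied to participation rather than to exposure, and participation can end because of an adverse event. Taken together, these rules make scheduled safety coverage shortest in people who may have reacted to stimulation. Coverage is also short for someone who completes Visit 6 and is not reached for Visit 7, since after the second session that call is the only scheduled contact beyond the next morning.

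What is at stake is the completeness of the adverse-event record. Section 2.2 presents the pilot as preparation for a full-scale trial in mild cognitive impairment, and its tolerability record will inform that trial. A record that is thinnest where stopping was related to safety is harder to interpret.

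**Working it through.** The plan states no length of safety follow-up, so there is no figure to reproduce. The check counts days from the visit schedule.

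**Inputs (7.1 and 7.4).** Take Visit 2 (first stimulation) as day 0. Then Visit 3 is day 1, Visit 4 is day 5, Visit 5 (second stimulation) is day g with g from 6 to 9, Visit 6 is day g + 1, and Visit 7 is day g + 5. Under 12.4 each visit asks back to the previous one.

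**Formula.** Scheduled coverage after a stimulation = day of the last attended visit − day of that stimulation.

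| Path | Days after session 1 | Days after session 2 |
|---|---|---|
| All visits attended | g + 5 = 11–14 | (g + 5) − g = 5 |
| Misses Visit 4, continues | 11–14 | 5 |
| Misses Visit 7 | g + 1 = 7–10 | (g + 1) − g = 1 |
| Leaves at Visit 2 after TMS or tACS | 0 | none given |
| Last attended visit is Visit 3 | 1 − 0 = 1 | none given |
| Last attended visit is Visit 4 | 5 − 0 = 5 | none given |
| Excluded at Visit 5 before stimulation | g = 6–9 | none given |
| Leaves at Visit 5 after stimulation | g = 6–9 | g − g = 0 |

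Section 4 gives the gap between sessions as 5–9 days. With g = 5 the lower ends 11, 7 and 6 become 10, 6 and 5; the session 2 column does not change.

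**Who is affected.** After the last exposure, coverage falls from 5 days to 0 or 1 for people who leave on the day of a stimulation or the day after, and for people who miss Visit 7. Three groups are not affected:
- participants who miss only Visit 4 and continue, because Visit 5 covers the gap;
- participants who leave before any TMS or tACS, for example at the first question of Visit 2;
- participants excluded at Visit 5 before stimulation, whose last exposure was 6–9 days earlier.

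**Do other provisions fill the gap?**
- Section 12.3 allows reports between visits, but this is passive, and the same section asks for documentation of events that occur on study.
- Sections 12.3 and 12.4 require recorded events to be followed until they resolve. This covers known events, not a new one after exit.
- The contact attempt in 7.6 applies to no-shows. The section mentions reasons for drop-out but no adverse-event enquiry, and it does not reach people stopped or excluded on site.
- Section 5.1.2 counts Visits 4 and 7 toward completion, but its remedy for a missing visit is replacement, not a safety contact.

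**Step lists.** The numbered steps for Visits 3 and 6 contain no adverse-event item, although 7.1 and 12.4 require one. Visit 3 opens with "Questioning whether there has been any use of alcohol, psychotropic substances or illicit drugs during the past 24 hours. If yes, the participant is excluded", so the list does not show when the safety question is put to someone excluded at that step.

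**The case against.** The strongest reply has four parts.

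First, the statement in 7.5 defines who counts as a completer. It does not tell staff to omit the calls, which stay on the schedule with their safety item, and 5.1.2 treats them as required. This stands in part: the two sections must be reconciled. Neither, however, provides a safety contact for someone who has left.

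Second, a person stopped for an adverse event already has that event on record and followed. This also stands. What remains uncovered is a new and different event that begins after exit.

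Third, a reader might infer from the step lists that nobody asks about adverse events after session 2 unless Visit 7 takes place. The documents do not support that. The Table of Events and 12.4 require an enquiry at Visits 3 and 6, 12.1 adds a stimulation questionnaire after each session, and nothing says that exclusion cancels the enquiry. The omission is a drafting gap.

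Fourth, no aim estimates an adverse-event rate. Section 12.1 describes tACS effects as mild and short-lived, and says there is no evidence tying the infrequent reports of headache, altered mood, changed cognition or sleepiness to stimulation rather than to taking part. So the documents do not show that late events would occur, and a claim that the record will be biased low by some amount goes too far. Nor do they give a safety reason for 5 days; it is simply the interval at which the plan already schedules its adverse-event calls.

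**Conclusion.** The point holds as a modest, cheaply corrected weakness in adverse-event capture. Scheduled coverage after the last exposure falls from 5 days to 0–1 day for exposed participants who leave on the day of a stimulation or the day after, or who miss Visit 7. Because discomfort or an adverse event can itself end participation, the shortfall can be related to the safety outcome.

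This rests on two assumptions: that 12.4 and the Table of Events are followed at every attended visit, and that the undefined last day of participation means the day on which the participant leaves or is last seen.

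The number of people affected cannot be derived. A reader might subtract the 28 completers from the 50 enrolled, but 5.1.2 gives 50 as a ceiling for IRB approval, 5.4 expects few drop-outs, and some would leave before any exposure. No efficacy analysis or sample-size figure is touched.

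**What to change.** 1. In 12.4, define the recording window as consent until 5 days after the last TMS or tACS exposure, regardless of discontinuation or replacement.
2. In 7.5, keep recall at Visits 4 and 7 non-mandatory if that is intended, but require attempts to complete the adverse-event item by telephone for every exposed participant who leaves early or misses Visit 7.
3. Reconcile 5.1.2 with 7.5 on whether Visits 4 and 7 count toward completion.
4. Add to the Visit 3 and Visit 6 step lists, ahead of the exclusion question, the adverse-event enquiry that 7.1 and 12.4 already require.

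The cost is protocol wording and one short call, of a kind already scheduled, for each exposed early leaver or missed Visit 7. No new procedure or staff is needed.
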